7 SAFETY MONITORING

An interim analysis (for both safety and efficacy) will be conducted after half of the patients in the dose expansion part in each group have been treated for 3 cycles. This is detailed in section 8.

8 INTERIM ANALYSES

There will be an interim analysis performed at the end of Part 1.

In the dose expansion part, after half of the patients in all groups (i.e. 9 patients per group) have been included and treated for 3 cycles, efficacy and safety will be analysed. If no response (as per RECIST v1.1) is seen during the interim analysis for at least one patient regardless of group, or for safety reasons, recruitment could be stopped (or the dose reduced) following discussion between the Investigator, the SMC and the Sponsor.

If there are no safety concerns and a response is seen, the study will continue until 18 patients have been recruited in each group.

9 DATA

9.1 CRF DATA

Data captured in the CRF will be provided by Simbec-Orion Data Management to the Statistics department as SAS datasets in a standard format which will be used for programming the outputs to be included in the Clinical Study Report (CSR). Analysis dataset and tables, figures and listings (TFL) programming will begin when populated SAS datasets are available.

9.2 EXTERNAL DATA

9.2.1 Laboratory Data

Transfers of safety laboratory data will be available from External Laboratories, delivered to Simbec-Orion Data Management via electronic transfer and stored within the study database. Details of laboratory data will be documented in the Data Management Plan (DMP). Either final data or a populated test transfer will be received before programming on laboratory data can begin.

The following results will be included (performed locally):

- **Haematology:** Haemoglobin, haematocrit, mean corpuscular volume, white blood cell differentials (neutrophils, basophils, eosinophils, lymphocytes and monocytes), Platelet count.
- **Serum Chemistry:** albumin, amylase, alkaline phosphatase, ALT, AST, urea, calcium, chloride, creatinine, creatinine clearance, CK, GGT, glucose, magnesium, phosphorus, potassium, sodium, total bilirubin, total protein, LDH, Lipase, CRP.
- **Urinalysis:** pH, Specific gravity, Ketones, Leucocytes, Protein, Glucose, Bilirubin, Urobilinogen, Blood, Sediment (if dipstick results are positive).

- **Coagulation:** INR, D-Dimer, AT, aPTT, TT, Fibrinogen.
- **Hormones:** β HCG (women of childbearing potential), LH, FSH, TSH, GH, PRL, ACTH.
- **Autoimmunity:** ANA, Anti-thyroglobulin, RF, ASMA.
- **Tumor markers:** CEA, CYFRA21-I, CA19-9, NSE, CA15-3, TPA.

9.2.2 Other non-CRF data

None

9.3 RANDOMISATION LIST

Not applicable.

9.4 PROGRAMMING AND DATA REVIEW

Programming of datasets, tables, figures and listings will be ongoing while study data management activities are in progress.

Prior to DBL, a review of the clinical database will be conducted. Listings for the data review will be produced. A DRM will be held to discuss the outcome of this review, any potential impact on the analyses, analysis sets and protocol deviations. Meeting minutes will be created and, once all data issues have been resolved, the analysis sets approved and protocol deviation classifications agreed, the database will be locked. These minutes will be finalised and signed off prior to DBL. Once the aforementioned actions have taken place the database can be locked. The post-lock analysis datasets will be generated, the TFLs will be run and quality control (QC) will take place.

10 STATISTICAL METHODS

10.1 GENERAL PRINCIPLES

- All statistical methods will be based on the International Conference on Harmonisation (ICH) E9 document “Statistical Principles for Clinical Trials”.
- All data collected will be presented within data listings.
- Generally, data listings will be sorted by subject and by period/regimen where appropriate.
- Generally, data will be summarised by period/cohort. Baseline data will be summarised overall. The format of the summaries is defined in the shells at the end of this document.
- Repeated visits will be denoted with ‘RPT’. Unscheduled visits will be denoted with ‘UNS’.
- In summary and analysis tables of continuous variables, standard descriptive statistics (N [number within analysis set, or group, or subgroup], n [number of observations included in analysis], mean, standard deviation [SD], median, minimum and maximum) will be presented. Least squares means (LSMean) and 95% confidence intervals (CI) will be presented in the

statistical analysis outputs as appropriate. For PK summaries, geometric mean and coefficient of variation (%CV) will also be used to summarise the data.

- Unless otherwise specified, the minimum and maximum statistics will be presented in summary tables to the same number of decimal places as the original data. The mean, median, LSMeans, and CI will be presented to one more decimal place than the original data. SD will be presented to two more decimal places than the original data.
- Derived PK parameters and concentration data listings and summaries will be presented to 3 significant figures (with the exception of CV%, which will be presented to 1 decimal place). The ratio of the geometric LSMeans and its associated confidence interval will be presented to 2 decimal places.
- In summary tables of categorical variables, the number of non-missing observations by category will be presented along with percentages. Unless otherwise specified, the denominator for each percentage will be the number of non-missing observations.
- All percentages will be presented to one decimal place.
- All plots will use a linear time scale for the nominal times of the visits and will be labelled by time point.
- For post-IMP assessments, only data obtained from scheduled visits/time points will be used in summary tables. Post-IMP repeat or unscheduled assessments will be listed only. For assessments occurring prior to IMP use (i.e. Screening, Day -1), the last repeat assessment for each visit will be included in the summary tables and, where repeats of baseline values occur, the last assessment will be used to calculate change from baseline. The derived baseline will be presented for each subject within the data listings and included within the summary tables.
- Dates and times for all output presentations will be presented as captured in the database.
- All statistical analysis will be performed using SAS 9.4 or higher.
- Generally, character values will be left aligned and numeric values will be decimally aligned.
- If no data is available for a specific output, the output will be produced stating an appropriate message indicating no data was present.
- If any of the assumptions underlying the formal statistical methods proposed are violated during the analysis of the final data, alternative statistical methods will be used and any changes documented in the statistical methods section of the clinical study report (CSR), including the rationale for use.
- For numeric data which includes non-numeric values (e.g. laboratory results reported as <10 or >100), results reported as $<x \leq x$, $\geq x >x$ will be treated as x for inclusion within the summaries/statistical analysis but will be listed as reported.

10.2 STRATIFICATION AND COVARIATE ADJUSTMENT

Not applicable.

10.3 INTERACTIONS

Not applicable.

10.4 MISSING DATA

No methods to account for missing safety data will be used.

10.5 POOLING OF SITES

Not applicable.

10.6 MULTIPLE COMPARISONS

Not applicable.

10.7 SUBGROUP ANALYSES

Not applicable.

10.8 STATISTICAL ISSUES

None.

11 STATISTICAL OUTPUT

General principles for layout of the statistical output are described in Section 10.1. Layout and specifications are illustrated for each unique table in the table shells in Section 14.

11.1 SUBJECT DISPOSITION

The subject disposition table will summarise the following data:

- The number of subjects receiving IMP under each dose level
- The number (%) of subjects who withdrew from the study and the associated reasons for withdrawal and timing of withdrawal.
- The number (%) of subjects in each analysis set

Screening and study completion/termination data (including informed consent information) will also be listed. A listing of all protocol deviations will be presented including major/minor classification. A data classification. A data listing presenting subject eligibility for each analysis set and the reason for exclusion from an analysis set will also be presented.

Disposition data will be summarised and listed using the All Patients Set (APS) population.

11.2 SUBJECT CHARACTERISTICS AT BASELINE

11.2.1 Demographic and Baseline Characteristics

Demographic data will be listed and descriptive statistics (N, n, arithmetic mean, standard deviation (SD), minimum, median and maximum) for the continuous variables age, height, weight and number of pre-treatments per patient at Screening and frequencies (n, %) for the categorical variables race and gender will be tabulated.

Demographic data will be listed and summarised using the Safety Set and the FAS.

11.3 EFFICACY ANALYSES

The primary efficacy endpoint of the study will be:

- Anti-tumour activity will be assessed by PFS using RECIST v1.1 assessed by the Investigator.

Secondary endpoints are:

- DOR
- DCR
- TTR
- TTP
- ORR

- OS (only Part 2).

All efficacy endpoints will be summarised and analysed descriptively, using the FAS and SAF populations. Kaplan Meier plots will be presented for time to event endpoints. Waterfall plots will be presented for RECIST data. The primary efficacy analysis will be repeated using the PP set.

Quality of Life Questionnaire:

Absolute values and change from baseline for total score will be presented using descriptive statistics for QoL Questionnaire scores. Overall there are 30 questions.

Only physical, emotional, fatigue and global related scores will be summarized.

Physical Functioning related questions are: Q1, Q2, Q3, Q4, Q5.

Emotional Functioning related questions are: Q21, Q22, Q23, Q24.

Fatigue relates questions are: Q10, Q12, Q18.

Global questions are: Q29, Q30.

Grouped scores for physical, emotional, fatigue, global scales and total scores will be normalised to the range 0-100 prior to being summarised.

All questions with the corresponding scores will be listed.

Other analysis:

- OMO-103 dosing will be summarised and listed using the SAF.

11.4 PK ANALYSES

No pk analysis will be perform by Simbec-Orion.

11.5 SAFETY ANALYSES

11.5.1 Adverse Events

All adverse events (AEs) will be coded using the Medical Dictionary for Regulatory Activities (MedDRA) dictionary version 24.0.

All AEs, including those which occurred prior to the first IMP use, will be listed. Only treatment emergent adverse events (TEAEs), i.e., existing conditions that worsen or events that occur during the course of the study after first IMP use, will be included within the summary tables. AEs that occur intermittently will be reported as separate events.

Adverse events will be summarised by

- Summary of Treatment Emergent Adverse Events
- Summary of Treatment Emergent Adverse Events – Event Count

- Summary of Treatment Emergent Adverse Events by System Organ Class and Preferred Term
- Summary of Treatment Emergent Adverse Events by System Organ Class and Preferred Term – Event Count
- Summary of Treatment Emergent Adverse Events by Preferred Term
- Summary of Treatment Emergent Adverse Events by Severity, System Organ Class and Preferred Term
- Summary of Treatment Emergent Adverse Events by Relationship to IMP, System Organ Class and Preferred Term

A subject with multiple occurrences of any AE is counted only once at the maximum level of severity or the strongest relationship to IMP.

The number of TEAEs and the number and % of subjects reporting at least 1 TEAE will be tabulated by system organ class (SOC) and preferred term (PT). A subject reporting multiple episodes of a particular AE will only contribute 1 count towards the corresponding SOC and PT.

In order to highlight the most frequently reported TEAEs, the number of TEAEs and the number and % of subjects reporting at least 1 TEAE will be tabulated by PT in order of descending frequency of subjects then events. A subject reporting multiple episodes of a particular AE will only contribute 1 count towards the corresponding PT.

The derived variable, 'Duration' will be presented where full date (events => 1 day) and time (events < 1 day) are present. If partial dates or times are present for any parameter required in the calculation, the variable will not be populated. The following will be used to calculate the variables:

Duration: (events => 1 day) (Date of Resolution – Date of Onset) ;

(events < 1 day) (Time of Resolution - Time of Onset) + 1 minute;

The derived variable 'Time from dose' will be assessed from the most recent infusion date and time. Where full date and time are present, both day from dose and time from dose will be presented. If partial dates are present for any parameter required in the calculation, only day from dose will be populated.

The following will be presented in listing format within the data summaries:

- Serious Adverse Events – If there are none present, the listing will be produced stating: '*No subjects experienced any serious adverse events.*'
- Adverse Events which Led to Withdrawal – If there are none present, the listing will be produced stating: '*No subjects experienced any adverse events that led to withdrawal.*'

Adverse event data will be listed and summarised using the Safety Set.

11.5.2 Laboratory Data

Routine safety clinical laboratory tests will be carried out at Screening.

The laboratory parameters required for this study are listed in section 9.2.1.

Laboratory safety data listings will be presented in two ways:

- Out of range values - any values that fall outside of the normal/alert ranges based on the reference ranges provided by the local/central laboratory (presented in listing format within the data summaries)
- All safety laboratory data (including physician's review (Normal, Abnormal-NCS, Abnormal-CS)) with any out of range values flagged (presented within the data listings).

Pregnancy test, post-menopausal assessment and any unplanned laboratory parameters will also be listed.

If there are no further parameters databased other than those specified in section 9.2.1 then the 'Other Laboratory Data' listings should display, '*No other laboratory parameters to report.*'

Laboratory data will be listed using the Safety Set.

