	
Secondary (Part 2: Dose Expansion):
 
 
• To confirm the RP2D and dosing regimen of OMO-103 for further development.
 
• To assess the type, incidence, severity, timing, seriousness, and relatedness of AEs and laboratory abnormalities.
 
• To characterise the PK of OMO-103.
 
• To assess other efficacy parameters in patients with advanced solid tumours including DCR, PFS, OS, TTP, TTR and DOR by RECIST v1.1.
 
• To assess the development of human ADA to OMO-103.
 
 
Exploratory (Both Parts 1 and 2):
 
 
• Evaluation of biomarkers.
 
• Myc expression levels.
 

Study design:	
This study is an open label, two-part, FIH Phase 1/2 dose-finding study designed to determine the safety, tolerability, PK, PD and proof-of-concept of OMO-103 in patients with advanced solid tumours.
 
The study consists of two parts:
 
 
• Part 1: Dose escalation in patients with advanced solid tumours, including 5 OMO-103 dose levels. Approximately 11 to 24 patients in total will be enrolled in Part 1, covering 5 dose levels with the primary objective of determining the safety and tolerability of OMO-103 and defining an appropriate dose for further evaluation in Part 2. The study will start with an accelerated-titration dose-escalation scheme enrolling one evaluable patient per cohort for the first 2 dose levels followed by a classic 3+3 design.
 
• Part 2: Dose expansion where at least 3 parallel groups of patients with advanced NSCLC, TNBC and CRC will be treated at the RP2D of OMO-103 to further characterise the safety, tolerability, PK, PD and anti-tumour activity of OMO-103. Approximately 18 patients will be enrolled in each of the 3 parallel groups of patients (NSCLC, TNBC, CRC) in Part 2. Note: If an objective response is observed in a tumour group within Part 1, or a long period without disease progression is observed (in Part 1), additional tumour groups may be added in this Phase 1/2 study for further assessment.
 

Diagnosis and main criteria for inclusion:	
Male or female patients, 18 years of age or older who sign the informed consent document, are willing and able to comply with the study protocol and have:

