2 STUDY OBJECTIVES

Part 1 – Dose Escalation

Primary Objective:

- To evaluate the safety and tolerability of OMO-103 in adult patients with advanced solid tumours.

Secondary Objectives:

- To establish and confirm the recommended Phase 2 dose (RP2D) and dosing regimen of OMO-103 for further development.
- To characterise the pharmacokinetics (PK) of OMO-103.
- To evaluate preliminary anti-tumour activity in the dose escalation part.
- To assess the development of human anti-drug antibodies (ADA) to OMO-103.

Part 2 – Dose Expansion

Primary Objective:

- To assess the preliminary anti-tumour activity of OMO-103 monotherapy as measured by progression free survival (PFS) according to standard criteria (Response Evaluation Criteria in Solid Tumours [RECIST] v1.1 [Eisenhauer 2009]).

Secondary Objectives:

- To confirm the RP2D and dosing regimen of OMO-103 for further development.
- To assess the type, incidence, severity, timing, seriousness, and relatedness of adverse events (AEs) and laboratory abnormalities.
- To characterise the PK of OMO-103.
- To assess other efficacy parameters in patients with advanced solid tumours including disease control rate (DCR), objective response rate (ORR), overall survival (OS), time to progression (TTP), time to response (TTR) and duration of response (DOR) by RECIST v1.1.
- To assess the development of human ADA to OMO-103.
- To evaluate the effect of OMO-103 on Quality of Life (QoL) measured by the Quality of Life questionnaire.

Exploratory (Both Parts 1 and 2):

- Evaluation of potential biomarkers.
- Myc expression levels.

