14.2 Efficacy Data

14.2.1 Efficacy parameters

Table 14.2.1.1	Summary of PFS	Safety Set
Table 14.2.1.2	Summary of PFS	Full Analysis Set
Table 14.2.1.3	Summary of PFS	Per Protocol Set <Part 2 only>
Table 14.2.2.1	Summary of Efficacy parameters, DCR, ORR, OS, TTP, TTR and DOR	Safety Set
Table 14.2.2.2	Summary of Efficacy parameters, DCR, ORR, OS, TTP, TTR and DOR	Full Analysis Set
Table 14.2.2.3	Summary of Efficacy parameters, DCR, ORR, OS, TTP, TTR and DOR	Per Protocol Set <Part 2 only>
Table 14.2.5	Dosing of OMO 103-01	Safety Set
Table 14.2.6	Change from Baseline: Quality of Life Questionnaire	Safety Set
Figure 14.2.6.1	Kaplan-Meier Plot of Time from Start of IMP to TTP	Full Analysis Set
Figure 14.2.6.2	Kaplan-Meier Plot of Time from Start of IMP to TTP	Per Protocol Set <Part 2 only>
Figure 14.2.7.1	Kaplan-Meier Plot of Time from Start of IMP to TTR	Full Analysis Set
Figure 14.2.7.2	Kaplan-Meier Plot of Time from Start of IMP to TTR	Per Protocol Set <Part 2 only>

I4.3 Safety Data**I4.3.1 Adverse Events**

Table I4.3.1.1	Summary of Treatment Emergent Adverse Events	Safety Set
Table I4.3.1.1a	Summary of Treatment Emergent Adverse Events – Event Count	Safety Set
Table I4.3.1.2	Summary of Treatment Emergent Adverse Events by System Organ Class and Preferred Term	Safety Set
Table I4.3.1.2a	Summary of Treatment Emergent Adverse Events by System Organ Class and Preferred Term – Event Count	Safety Set
Table I4.3.1.3	Summary of Treatment Emergent Adverse Events by Preferred Term	Safety Set
Table I4.3.1.4	Summary of Treatment Emergent Adverse Events by Severity, System Organ Class and Preferred Term	Safety Set
Table I4.3.1.5	Summary of Treatment Emergent Adverse Events by Relationship to IMP, System Organ Class and Preferred Term	Safety Set
Table I4.3.1.6	Serious Adverse Events	Safety Set
Table I4.3.1.7	Adverse Events Leading to Withdrawal	Safety Set

I4.3.2 Laboratory Safety

Table I4.3.2.1	Biochemistry Out of Normal Range Data	Safety Set
Table I4.3.2.2	Haematology Out of Normal Range Data	Safety Set
Table I4.3.2.3	Urinalysis Abnormal Values	Safety Set
Table I4.3.2.4	Autoimmune Values	Safety Set
Table I4.3.2.5	Frequency of Autoimmune Values	Safety Set

I4.3.3 ECG Data

Table I4.3.3.1	Statistical summaries of ECG parameters by visit	Safety Set
----------------	--	------------

I4.3.4 ECOG Performance Status

Table I4.3.4.1	Statistical summaries of ECOG status by visit	Safety Set
----------------	---	------------

I4.3.5 Vital Signs

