Subject	Visit/ Time Point	Sample Date/Time	Sample ID	Parameter	Result	Unit	Flag	Normal Range	
								Low	High
xxx	xxxxxx	xxxxxxxxxx	xxxxx	xxxxxxx	x.xx	xxx	x	x.x	x.xx
				xxxxxxx	x.xx	xxx	x	x.x	x.xx
				xxxxxxx	x.xx	xxx	x	x.x	x.xx
				xxxxxxx	x.xx	xxx	x	x.x	x.xx
	xxxxxx	xxxxxxxxxx	xxxxx	xxxxxxx	x.xx	xxx	x	x.x	x.xx
				xxxxxxx	x.xx	xxx	x	x.x	x.xx
				xxxxxxx	x.xx	xxx	x	x.x	x.xx
				xxxxxxx	x.xx	xxx	x	x.x	x.xx
	xxxxxx	xxxxxxxxxx	xxxxx	xxxxxxx	x.xx	xxx	x	x.x	x.xx
				xxxxxxx	x.xx	xxx	x	x.x	x.xx
				xxxxxxx	x.xx	xxx	x	x.x	x.xx
				xxxxxxx	x.xx	xxx	x	x.x	x.xx

Source Listing: 16.2.9.1; Produced: yyyy-mm-ddThh:mm - Page x of y
H = Above Normal Range; Lo = Below Normal Range.

Programming Note: This table will be repeated for Part 2. Similar tables will be produced for Hematology Out of Normal Range Data - Part 1 and Part 2 (Table 14.3.2.2) and Urinalysis Out of Normal Range Data (Table 14.3.2.3).

OMO-103-01
Table 14.3.2.4
Autoimmune values - Part 1
Safety Set

<Parameter (<units>>						
Visit/ Time Point	n	Mean	SD	Min	Median	Max
SCREENING	x	x.xx	x.xxx	x.x	x.xx	x.x
CYCLE 3 DAY 01	x	x.xx	x.xxx	x.x	x.xx	x.x
CYCLE 4 DAY 01	x	x.xx	x.xxx	x.x	x.xx	x.x
...						

Source Listing: Listing 16.2.9.5; Produced: yyyy-mm-ddThh:mm - Page x of y

Programming Note: This table will be repeated for Part 2.

OMO-103-01
Table 14.3.2.5
Frequency of Autoimmune values - Part 1
Safety Set

<Parameter (<units>>		COHORT 1 (Dose xx mg/ml) (N=x)	Overall (N=x)
SCREENING	N	x (x.x)		x (x.x)
	Positive	x (x.x)		x (x.x)
	Negative	x (x.x)		x (x.x)
CYCLE 3 DAY 01	N	x (x.x)		x (x.x)
	Positive	x (x.x)		x (x.x)
	Negative	x (x.x)		x (x.x)
CYCLE 4 DAY 01	N	x (x.x)		x (x.x)
	Positive	x (x.x)		x (x.x)
	Negative	x (x.x)		x (x.x)

Source Listing: 16.2.9.5; Produced: yyyy-mm-ddThh:mm - Page x of y

Programming note: A similar table will be presented for Part 2

OMO-103-01
Table 14.3.3.1
Summary of 12-Lead ECG Data - Part 1
Safety Set

Visit/ Time Point		COHORT 1 (Dose xx mg/ml) (N=x)	Overall (N=x)
SCREENING	N	x (x.x)		x (x.x)
	Normal	x (x.x)		x (x.x)
	Abnormal NCS	x (x.x)		x (x.x)
	Abnormal CS	x (x.x)		x (x.x)
TREATMENT PERIOD	N	x (x.x)		x (x.x)
	Normal	x (x.x)		x (x.x)
	Abnormal NCS	x (x.x)		x (x.x)
	Abnormal CS	x (x.x)		x (x.x)
FOLLOW-UP PERIOD	N	x (x.x)		x (x.x)
	Normal	x (x.x)		x (x.x)
	Abnormal NCS	x (x.x)		x (x.x)
	Abnormal CS	x (x.x)		x (x.x)

Source Listing: 16.2.12.1; Produced: yyyy-mm-ddThh:mm - Page x of y

Programming note: A similar table will be presented for Part 2

OMO-103-01
Table 14.3.4.1

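### Apart from autoimmunity, the SAP plans no summary of the incidence or severity of laboratory abnormalities, although this is a stated Part 2 secondary objective

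*SAP*

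**What the plan says.** The objective appears in both documents. The protocol synopsis gives it among the Part 2 secondary objectives as "To assess the type, incidence, severity, timing, seriousness, and relatedness of AEs and laboratory abnormalities". SAP section 2 repeats it: "To assess the type, incidence, severity, timing, seriousness, and relatedness of adverse events (AEs) and laboratory abnormalities".

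SAP 11.5.2 describes the laboratory output. It opens with "Laboratory safety data listings will be presented in two ways". The first way is values outside the reference range, shown as a listing within the data summaries. The second is "All safety laboratory data (including physician's review (Normal, Abnormal-NCS, Abnormal-CS)) with any out of range values flagged". The section closes with "Laboratory data will be listed using the Safety Set".

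The list of tables in SAP section 14 has five entries under laboratory safety. Three are of the type "Biochemistry Out of Normal Range Data" (Tables 14.3.2.1 to 14.3.2.3, for biochemistry, haematology and urinalysis). The other two cover autoimmunity: descriptive statistics in Table 14.3.2.4, and "Frequency of Autoimmune Values" in Table 14.3.2.5.

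The section 15 shell shared by the first three tables carries subject, visit, sample, parameter, result, unit, flag and normal range. Its footnote defines the flag as "H = Above Normal Range; Lo = Below Normal Range".

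**The concern.** Incidence needs a count of patients over a denominator, and severity needs a grade. For routine laboratory safety the plan provides neither. Someone who runs the SAP exactly as written will have long listings, but no table of how many patients in a tumour group developed, say, a raised transaminase or a low platelet count, or how severe it was.

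The protocol synopsis uses integrated safety data twice: to choose the expansion dose, and at the end of the study to settle the RP2D. If rates are counted only after the data are seen, the choice of parameters, thresholds, denominators and handling of baseline is made at that point too. Pre-specifying a table removes that freedom.

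**Working it through.** The documents state no figure on this point, so there is nothing to reproduce. The check sets the objective against the planned output.

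**Step 1: what the objective needs against what each output gives.**

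| Laboratory data (SAP 9.2.1) | Planned output (SAP 14, 15) | Patient n and % | Grade | Tabulated change from baseline |
|---|---|---|---|---|
| Biochemistry | Table 14.3.2.1, Listing 16.2.9.1 | No | No | No |
| Haematology | Table 14.3.2.2, Listing 16.2.9.2 | No | No | No |
| Urinalysis | Table 14.3.2.3, Listing 16.2.9.3 | No | No | No |
| Coagulation | None named | No | No | No |
| Autoimmunity | Tables 14.3.2.4 and 14.3.2.5 | Yes (14.3.2.5) | No | No |

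Of the five laboratory safety tables, three are listings, two are summaries (both of autoimmunity) and none is graded. Coagulation might be placed under the listing for other laboratory data (16.2.9.5). However, SAP 11.5.2 reserves that listing for parameters beyond those in 9.2.1, and coagulation is in 9.2.1.

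**Step 2: is listing without summary the SAP's general approach?** It is not. Sections 11.5.3, 11.5.5 and 11.5.6 have vital signs, physical examination and ECOG status summarised and listed. Section 11.5.4 has ECG parameters in a shift table and listed. SAP 10.1 says data are generally summarised by period or cohort. The protocol synopsis, under general considerations, has all data summarised descriptively by dose cohort and, where applicable, by expansion group. SAP 1.2 declares two changes from the protocol (the Part 2 primary endpoint and the number of dose levels). Neither concerns laboratory data.

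**Step 3: can the flag stand in for a new or worsened abnormality?** The inclusion criteria admit AST and ALT up to 2.5 x ULN, or 5 x ULN with liver metastases. They also admit total bilirubin up to 1.5 x ULN (higher if direct bilirubin is not above the ULN) and aPTT up to 1.5 x ULN. Each of these allows a value above the normal limit at entry. Take two patients with liver metastases: one enters at 4 x ULN and stays there, the other rises from normal to 4 x ULN. Both are flagged high on treatment. Only a comparison with baseline separates them, and no planned table makes it.

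**Step 4: what a summary would show.** SAP 3.4 gives about 18 patients per group, so 3 x 18 = 54 in Part 2. Illustrative exact (Clopper-Pearson) 95% intervals for assumed counts are:

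- 0/18: 0% (0 to 18.5%)
- 2/18: 11.1% (1.4 to 34.7%)
- 5/54: 9.3% (3.1 to 20.3%)

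With an assumed true rate of 10%, the chance of at least one case is 1 - 0.9^18 = 85% in one group and 1 - 0.9^54 = 99.7% overall. A summary would be imprecise within a group but informative overall, so a pooled Part 2 column is worth having.

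**The case against.** The strongest reply is that the objective is a single phrase covering AEs and laboratory abnormalities, and that seriousness and relatedness are attributes of AEs. On that reading, abnormalities that matter are meant to be assessed through AE reporting, and the TEAE tables give counts and percentages by grade, relationship, organ class and preferred term. This stands in part. How far it goes depends on the rule for when a laboratory value must be reported as an AE, and the protocol text available here (the synopsis) does not contain that rule. If nearly all graded abnormalities must be reported, the gap is small. If only those judged clinically significant are reported, most of it remains. Either way, the objective names laboratory abnormalities in addition to AEs.

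Two stronger readings are tempting, and the documents support neither.

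- A reader might infer that only out-of-range values will be shown. In fact every laboratory value is also listed, with the physician's review, and autoimmunity has its own frequency table.
- A reader might infer that the objective cannot be answered at all. Visit and sample dates are in the listings, counts could be made from them by hand, and SAP 10.1 says the derived baseline will appear in the listings (although the biochemistry listing shell has no column for it). What is missing is a pre-specified summary.

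It is also fair to say that the study is exploratory with no formal sizing, that the first two dose levels have one evaluable patient each, so percentages there add little to a listing, and that safety data are reviewed continuously.

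**Conclusion.** The point holds as a reporting gap and should be corrected. For haematology, biochemistry, urinalysis and coagulation, no planned output gives the number and percentage of patients with an abnormality or its grade, and no grading scale for laboratory values is named in the text available. The only exceptions are autoimmunity and whatever is recorded as an AE. This falls short of a secondary objective stated in both documents, and it departs from the protocol's general rule on summaries without being declared.

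The size is moderate. The data are collected and listed, no primary endpoint is touched, and nothing is lost that could not be tabulated later. The conclusion does not depend on any assumed rate. Its practical weight depends on the AE reporting rule, which could not be checked.

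**What to change.** In SAP 11.5.2, change the plan from listing to summarising and listing on the Safety Set, and add shells for the following:

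- **Gradable haematology, chemistry and coagulation parameters:** n/N (%) of patients by worst post-baseline grade on a named toxicity scale with its version, and a baseline-to-worst shift table. Grade high and low directions separately where both apply.
- **Urinalysis and parameters without a grade:** a normal/abnormal shift from baseline to worst.
- **Columns:** each dose cohort in Part 1; each tumour group and overall in Part 2.
- **Denominator:** define N for each parameter, for example patients with at least one post-baseline result, with a row for missing baseline.
- **Unscheduled results:** SAP 10.1 keeps post-dose repeat and unscheduled results out of summary tables. State an explicit exception so that they count towards the worst value, since an unscheduled sample may well hold it.

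Name an output for coagulation. Also reconcile the opening of 11.5.2, which places routine tests at screening, with the flow charts in SAP 3.3, which show safety blood sampling throughout treatment. Keep the existing listings as support.

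The cost is a few extra shells for both parts, derivation of grades from tests done locally at up to 15 centres with their own ranges, and the independent double programming that SAP section 12 requires. No additional samples or visits are needed.
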